3.2.2.2.2 Baseline Period

Baseline Period (-1h to 0h) begins 1 hour before and ends immediately prior to the first initiation of BRV infusion. The Baseline Period is included in the Screening Period.

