8.1.2 Baseline seizure burden

Baseline seizure burden is defined as seizure burden measured on the continuous VEEG (total ENS in minutes per hour) during a period of up to 1 hour immediately prior to the first administration of study medication.

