8.1.2.2 Baseline severe seizure burden

Baseline severe seizure burden is defined as seizure activity (total ENS duration in minutes) for >15 minutes in at least one of the following 30-minute time periods 0-30 and >30-60 minutes during the up to 1-hour Baseline Period. For example, if total ENS duration is 18 minutes and the distribution of ENS duration is 16 minutes in 0-30 minutes time period and 2 minutes in >30-60 minutes time period, then the baseline seizure burden is severe.

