8.1.4 Average per hour seizure burden (ENS in minutes per hour)

Average per hour seizure burden per subject (ENS in minutes per hour) is defined as total seizure burden measured over a period of time (in minutes) divided by the number of hours in the given period of time. That is all seizure activity times (durations in minutes) will be added up across the Evaluation Period. It will then be divided by the total duration of the Evaluation Period to calculate a seizure burden value in minutes per hour. Average seizure burden value will be calculated during the Baseline period and the Evaluation Period (and transformed the data by taking log (x +1) for both Baseline and the Evaluation Period if needed).

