8.1.5 Percent change in baseline seizure burden

Percent change in baseline seizure burden is defined as a difference between average per hour seizure burden at baseline (calculated over the 1-hour baseline period) and average per hour

seizure burden calculated over given period of time after the start of initial BRV treatment divided by the average per hour seizure burden at baseline and multiplied by 100.

If the percent change is $\geq 80\%$ (reduction in baseline) and baseline seizure burden is non-severe or if the percent change $\geq 50\%$ (reduction in baseline) and baseline seizure burden is severe then this subject is defined as **BRV responder**. No rounding will be applied, one decimal will be considered for comparison (for example, if the percent change is 79.999%, then consider 1 decimal as 79.9% which is less than 80%).

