8.2.4 Derivations of the secondary efficacy variables

The following secondary efficacy variables are defined as follows:

- Proportion of subjects with at least 80% reduction in non-severe seizure burden from Baseline to 3 hours after the initial BRV treatment [*derivations*: see the definition of baseline non-severe seizure burden in [Section 8.1.2.1](#); reduction of at least 80% in non-severe seizure burden from baseline is defined as a $\geq 80\%$ difference between average per hour seizure burden at baseline (calculated over the 1-hour Baseline Period) and average per hour seizure burden calculated over 3 hours after the start of initial BRV treatment divided by the average per hour seizure burden at baseline and multiplied by 100. The numerator is defined as the number of subjects with the 80% reduction described above. The denominator is defined as the number of subjects in the FAS from Confirmatory Cohorts with baseline non-severe seizure burden.]
- Proportion of subjects with at least 50% reduction in severe seizure burden from Baseline to 3 hours after the initial BRV treatment [*derivations*: see the definition of baseline severe seizure burden in [Section 8.1.2.2](#); reduction of at least 50% in severe seizure burden from baseline is defined as a $\geq 50\%$ difference between average per hour seizure burden at baseline (calculated over the 1-hour Baseline Period) and average per hour seizure burden calculated over 3 hours after the start of initial BRV treatment divided by the average per hour seizure burden at baseline and multiplied by 100. The numerator is defined as the number of subjects with the 50% reduction described above. The denominator is defined as the number of subjects in the FAS from Confirmatory Cohorts with baseline severe seizure burden.]

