- Absolute reduction in average seizure burden measured by continuous VEEG from Baseline to the end of the 96-hour Evaluation Period [*derivations*: see the definition of baseline seizure burden and of average per hour seizure burden in [Section 8.1](#), average per hour over 96-hour Evaluation Period seizure burden is calculated as the total seizure burden during the 96-hour Evaluation Period divided by 96, the number of hours in the Evaluation Period, average per hour seizure baseline seizure burden is calculated as the total seizure burden over 1-hour Baseline Period divided by 1. The **absolute reduction** in average per hour seizure burden is defined as the average per hour seizure burden at the end of the 96-hour Evaluation Period minus average per hour baseline seizure burden]

- Percentage reduction in average seizure burden measured by continuous VEEG from Baseline to the end of the 96-hour Evaluation Period [**derivations**: see the definition of baseline seizure burden and of average per hour seizure burden in [Section 8.1](#), average per hour over 96-hour Evaluation Period seizure burden is calculated as the total seizure burden during the 96-hour Evaluation Period divided by 96, the number of hours in the Evaluation Period, average per hour seizure baseline seizure burden is calculated as the total seizure burden over 1-hour Baseline Period divided by 1. The **percentage reduction** is defined as the absolute reduction in average per hour seizure burden divided by the average per hour baseline seizure burden and multiplied by 100.]
- Proportion of BRV responders during the 96-hour Evaluation Period (measured at the end of the 96-hour Evaluation Period) [**derivations**: see the definition of BRV responders for other than main efficacy variable in [Section 8.1](#), the post-baseline seizure burden will be evaluated during the last 1 hour of the 96-hour Evaluation Period, the denominator is defined as the number of subjects in the FAS from Confirmatory Cohorts.]

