- Rate of at least 50% reduction in ENS frequency per hour from Baseline to the end of the 96-hour Evaluation Period [**derivations**: the numerator is defined as the number of subjects with the 50% reduction in ENS frequency, i.e. the difference between the average ENS frequency

per hour at Baseline and the average ENS frequency per hour over the 96-hour Evaluation Period divided by the average per hour Baseline ENS frequency and multiplied by 100 should be at least 50%, the denominator is defined as the number of subjects in the FAS from Confirmatory Cohorts. Average per hour ENS frequency at Baseline is calculated as the total number of ENS over 1-hour Baseline Period divided by 1; average per hour ENS frequency at the end of the 96-hour Evaluation Period is defined as the number of ENS over 96-hour Evaluation Period divided by 96.]

- Proportion of subjects who are seizure-free by time interval at 3 hours, at 3-hour intervals thereafter through 24 hours, and every 12 hours to 24 hours following the start of the initial BRV treatment [*derivations*: the numerator is defined as the number of subjects with no ENS or 100% reduction in seizure burden from Baseline to 3 hours after the first BRV dose and then with no seizure burden at 6, 9, 12, 15, 18, 21, 24, 36, 48, 60, 72, 84, 96 hours after the first BRV dose, the 2 hours of VEEG prior to the defined time point will be evaluated for seizure freedom/ENS absence; the denominator is defined as the number of subjects in the FAS from Confirmatory Cohorts, see the definition of reduction in seizure burden from Baseline in [Section 8.1](#).]
- Absolute difference in clinical seizures (annotated by central reader) at the end of the first 24-hour of the 96-hour Evaluation Period from Baseline for neonates with motor seizures at the time of inclusion [*derivations: absolute difference* is defined as the difference between the number of clinical seizures observed during the 1-hour Baseline Period and the number of post-baseline clinical seizures observed during the 1 hour prior to the end of the 24-hour Evaluation Period]

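### SAP 8.2.4 divides Baseline seizure minutes and counts by a fixed hour, although neonates in status epilepticus may have a Baseline of only up to 30 minutes

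*SAP*

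**What the plan says.** **Length of Baseline.** SAP 2.3.2 and protocol 5.1.2 and 10.3 ask for at least an hour of recording in neonates with intermittent seizures, but up to 30 minutes in status epilepticus. Under protocol Table 5-2, footnote b, the status epilepticus recording can end once 15 minutes of unbroken seizure, or seizure activity for half the time, has been confirmed. SAP 8.1.2 accordingly measures Baseline burden "during a period of up to 1 hour immediately prior to the first administration of study medication", and SAP 8.1.2.2 grades severity "during the up to 1-hour Baseline Period".

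**Fixed hour.** SAP 3.2.2.2.2 says the "Baseline Period (-1h to 0h) begins 1 hour before and ends immediately prior to the first initiation of BRV infusion". SAP 8.2.4 turns this into arithmetic, for burden ("average per hour seizure baseline seizure burden is calculated as the total seizure burden over 1-hour Baseline Period divided by 1") and for counts ("Average per hour ENS frequency at Baseline is calculated as the total number of ENS over 1-hour Baseline Period divided by 1"). No exception is given for a shorter record.

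**One hour without a divisor.** SAP 8.1.5 and the first two variables in SAP 8.2.4 mention a one-hour Baseline only in passing, inside a bracket.

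**General rule.** SAP 8.1.4 has the total "divided by the number of hours in the given period of time" and, for the post-dose side, divides by the whole length of the Evaluation Period.

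**Post-dose.** SAP 8.2.4 divides 96-hour totals of minutes and counts by 96. For dropouts, SAP 4.2.3 points instead to the hours between the start of the Evaluation Period and withdrawal.

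**Sign.** For the two 96-hour burden variables, SAP 8.2.4 defines reduction as post-dose minus Baseline. SAP 8.1.5, the ENS-frequency variable in 8.2.4, and SAP 8.3.1 all use Baseline minus post-dose.

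**The concern.** A total collected over 30 minutes and divided by 1 hour is not an hourly rate. It treats the unrecorded half hour as free of seizures. The error always runs against response, and it falls on the subjects with the heaviest seizure activity, because only they may enter on a short record.

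The variables directly exposed are the absolute and percentage reductions in burden over 96 hours and the rate of at least 50% reduction in ENS frequency, all listed as secondary. Two programmers, one following SAP 8.1.2 and the other SAP 8.2.4, could report different values for the same subject. The clinical-seizure differences at 24 hours have a related weakness: undivided counts from the Baseline and from one post-dose hour are subtracted, which is not like for like if the Baseline lasted 30 minutes.

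**Working it through.** The documents give no result to reproduce on this point and no seizure data. The recorded lengths come from the documents; the seizure minutes, counts and withdrawal time below are illustrative assumptions.

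**Baseline divisor.** Let *m* be the recorded Baseline minutes and *b* the ENS minutes (or count) in them.

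- Rate on recorded time: B = 60*b*/*m*. Rate as written in 8.2.4: *b*/1 = B × *m*/60.
- With post-dose rate P, the reduction on recorded time is r = 1 − P/B.
- The reduction as written is 1 − (60/*m*)(1 − r).
- A written reduction of at least 50% therefore needs r ≥ 1 − *m*/120.

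| Recorded Baseline | Fall in recorded rate needed to compute as 50% |
|---|---|
| 60 min | 50% |
| 45 min | 62.5% |
| 30 min | 75% |
| 15 min | 87.5% |

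At 60 minutes the two rules agree.

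**ENS frequency.** 6 ENS in 30 minutes is 12 per hour on recorded time and 6 as written. With 4 per hour post-dose:

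- Recorded time: (12 − 4)/12 = 66.7%, which passes the 50% variable.
- As written: (6 − 4)/6 = 33.3%, which fails it.

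**96-hour burden.** 20 ENS minutes in 30 recorded minutes is 40 min/h on recorded time and 20 min/h as written. Post-dose, 960 minutes over 96 hours is 10 min/h. Using the post-dose-minus-Baseline sign in 8.2.4:

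- Recorded time: 10 − 40 = −30 min/h, and −30/40 = −75%.
- As written: 10 − 20 = −10 min/h, and −10/20 = −50%.

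Under the sign used elsewhere in the SAP these would be +75% and +50%, so a table built from 8.2.4 would print an improvement as a negative reduction.

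**Post-dose divisor.** Take a full one-hour Baseline at 20 min/h and a subject who leaves the study and VEEG at 24 hours with unchanged burden. The total is 20 × 24 = 480 minutes.

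- Divided by 96: 480/96 = 5 min/h, a computed fall of (20 − 5)/20 = 75%.
- Divided by observed hours: 480/24 = 20 min/h, a fall of 0%.

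The interruption allowance in protocol 5.1, 30 minutes a day, removes 4 × 0.5 = 2 hours. Then 94/96 = 0.979, so the rate is about 2.1% low.

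The two divisors err in opposite directions: a short Baseline hides benefit, and early loss of VEEG creates it.

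**The case against.** **The hour may be only a name, and may be filled.** SAP 2.3.2 lets suitable standard-of-care VEEG from before consent count towards Baseline, so some subjects in status epilepticus may have a full hour. That is permitted, not required. Reading one-hour as a label is reasonable for SAP 8.1.5, but it cannot explain an explicit division by 1.

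**SAP 8.1.4 does not settle the matter.** If its period is the one fixed in SAP 3.2.2.2.2, the divisor is 1. This stands. The firm conflict is with SAP 8.1.2, 8.1.2.2 and 2.3.2 and protocol 10.3.

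**The recorded rate is not the true rate.** A window that may close because seizures were confirmed can catch a peak: 15 ENS minutes in 15 recorded minutes scales to 60 min/h. This also stands and limits the remedy.

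**Short Baselines may not be analysed.** The Full Analysis Set asks for two hours of interpretable VEEG from both Baseline and the first three post-dose hours. If that means two hours from each, no short Baseline enters, though neither would a Baseline of exactly one hour. If it means two hours together, 30 minutes plus 1.5 hours is enough. The text does not decide.

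**Stronger readings that the documents do not support.**

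- A reader might infer that the fixed 96 contradicts SAP 8.1.4. It does not: 8.1.4 divides by the length of the Evaluation Period, which SAP 3.2.2.2.3 sets at 96 hours. The tension is with the loosely worded SAP 4.2.3, which could equally be read as overriding 96 for dropouts.
- A reader might infer that the fixed 96 distorts results for everyone who stops BRV. SAP 2.3.2 has those subjects complete the full 96 hours, so it matters only for study withdrawal, death or lost VEEG.
- A reader might infer that severity grading needs the same repair. It counts minutes within each 30-minute span and uses no hourly divisor.

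**Conclusion.** The Baseline rule in SAP 8.2.4 is wrong as written for any subject with less than an hour of Baseline VEEG. With 30 recorded minutes it halves the Baseline rate and raises the effective 50% bar to a 75% fall in the recorded rate. This is a misstated rule rather than missing detail, and it should be corrected before analysis.

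It is tempting to conclude that the main responder rate is understated. The documents do not establish this: SAP 8.1.5 gives no divisor, and SAP 8.1.1 and 8.1.2 express burden per hour. Only if 8.1.5 is read like 8.2.4 would a severe subject with 30 recorded minutes need a 75% fall; each subject changed would then move the rate by 1/36 = 2.8 percentage points, taking 36 analysed subjects.

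The fixed 96 and the reversed sign are lesser faults in the same derivations. No overall effect can be stated: the number of short Baselines is not given, pre-consent VEEG may fill the hour, and entry to the Full Analysis Set is ambiguous. Stakes are moderate, since SAP 4.5 treats all analyses as descriptive and plans no tests.

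**What to change.** - In SAP 3.2.2.2.2, define Baseline as up to one hour before the first BRV infusion.
- In SAP 8.1.5 and 8.2.4, divide Baseline ENS minutes and counts by the hours of Baseline VEEG actually recorded, and remove the division by 1.
- Put the Baseline clinical-seizure count in SAP 8.2.4 on the same per-hour basis.
- State that the observed-hours rule of SAP 4.2.3 replaces 96 for subjects who leave VEEG early.
- Define reduction as Baseline minus post-dose in the two 96-hour burden variables, as elsewhere in the SAP.
- Leave the severity rule in SAP 8.1.2.1 and 8.1.2.2 unchanged.
- Report how many Full Analysis Set subjects had under one hour of Baseline VEEG, and show the affected variables under both divisors as a sensitivity analysis.

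The cost is SAP wording and one derivation rule. VEEG start, stop, interruption and restart times are already among the items listed in SAP 10.4.7. The downside is that rates scaled up from short records are noisier and may overstate Baseline, and hence response, because the window can close once seizures are confirmed. Showing both divisors lets a reader judge this.

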4.2.2 Other efficacy variables

Other efficacy variables will include:

- Absolute reduction from Baseline in seizure burden at evaluation periods of 0 hours to 3 hours, >3 hours to 6 hours, >6 hours to 12 hours, >12 hours to 24 hours, >24 hours to 36 hours, >36 hours to 48 hours, >48 hours to 72 hours, and >72 hours to 96 hours after the start of initial BRV treatment
- Percent reduction from Baseline in seizure burden at evaluation periods of 0 hours to 3 hours, >3 hours to 6 hours, >6 hours to 12 hours, >12 hours to 24 hours, >24 hours to 36 hours, >36 hours to 48 hours, >48 hours to 72 hours, and >72 hours to 96 hours after the start of initial BRV treatment
- Categorized percentage reduction from Baseline to the end of the 96-hour Evaluation Period in seizure burden (<-25% [worsening], -25% to <25% [no change], 25% to <50%, 50% to <80%, and ≥80%)
- Proportion of BRV responders by time interval at evaluation periods of 0 hours to 3 hours, >3 hours to 6 hours, >6 hours to 12 hours, >12 hours to 24 hours, >24 hours to 36 hours, >36 hours to 48 hours, >48 hours to 72 hours, and >72 hours to 96 hours after the start of initial BRV treatment
- Proportion of subjects who switch over from BRV to another AED during the 96-hour Evaluation Period
- Proportion of responders to other treatment during the 96-hour Evaluation Period (including at the end of the 96-hour Evaluation Period, and by time intervals: 0 hours to 3 hours, >3 hours to 6 hours, >6 hours to 12 hours, >12 hours to 24 hours, >24 hours to 36 hours, >36 hours to 48 hours, >48 hours to 72 hours, and >72 hours to 96 hours after the start of initial BRV treatment)

(A responder to other treatment is defined as at least 80% reduction in nonsevere seizure burden from start of other treatment to end of other treatment or at least 50% reduction in severe seizure burden from the initiation of other treatment to end of other treatment during the 96-hour Evaluation Period).

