8.3 Statistical analysis of other efficacy variables

8.3.1 Derivations of other efficacy variables

The other efficacy variables are defined as follows:

- Absolute and percentage reduction from Baseline in seizure burden at evaluation periods of 0 hours to 3 hours, >3 hours to 6 hours, >6 hours to 12 hours, >12 hours to 24 hours, >24 hours to 36 hours, >36 hours to 48 hours, >48 hours to 72 hours, and >72 hours to 96 hours after the start of initial BRV treatment [*derivations*: see the definition of baseline seizure burden and of average per hour seizure burden in [Section 8.1](#), the **absolute reduction** is defined as the difference between the baseline average per hour seizure burden and average per hour seizure burden at evaluation periods of 0 hours to 3 hours, >3 hours to 6 hours, >6 hours to 12 hours, >12 hours to 24 hours, >24 hours to 36 hours, >36 hours to 48 hours, >48 hours to 72 hours, and >72 hours to 96 hours after the start of initial BRV treatment. The **percentage reduction** is defined as the absolute reduction in seizure burden divided by the baseline average per hour seizure burden and multiplied by 100.]
- Categorized percentage reduction from Baseline to the end of the 96-hour Evaluation Period in seizure burden (<-25% [worsening], -25% to <25% [no change], 25% to ≤50%, 50% to <80%, and ≥80%) [*Derivations*: The **percentage reduction** of seizure burden is defined as the difference between the average per hour baseline seizure burden and the average per hour seizure burden at the end of the 96-hour Evaluation Period divided by the average per hour baseline seizure burden and multiplied by 100. For the definition of the average per hour seizure burden, please see [Section 8.1](#).]
- Proportion of BRV responders by time interval at evaluation periods of 0 hours to 3 hours, >3 hours to 6 hours, >6 hours to 12 hours, >12 hours to 24 hours, >24 hours to 36 hours, >36 hours to 48 hours, >48 hours to 72 hours, and >72 hours to 96 hours after the start of initial BRV treatment [*derivations*: see the definition of BRV responders in [Section 8.1](#), for the numerator calculate the number of responders during the given above evaluation periods 0-3 hours, >3-6 hours, >6-12 hours, >12-24 hours, >24-36 hours, etc., the denominator is defined as the number of subjects in the FAS from Confirmatory Cohorts.]

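### SAP 8.2.4 derives the two 96-hour seizure-burden reductions with the opposite sign to the rest of the SAP, so improvement prints as a negative reduction

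*SAP*

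**What the plan says.** Protocol 4.2.1 and SAP 2.2.2.1 name two secondary efficacy variables: the absolute reduction and the percent reduction in average seizure burden from Baseline to the end of the 96-hour Evaluation Period.

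SAP 8.2.4 derives them as follows.

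- The absolute reduction "is defined as the average per hour seizure burden at the end of the 96-hour Evaluation Period minus average per hour baseline seizure burden".
- The percentage version "is defined as the absolute reduction in average per hour seizure burden divided by the average per hour baseline seizure burden and multiplied by 100".

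Other SAP derivations put Baseline first.

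- SAP 8.1.5, which feeds the responder rule: "Percent change in baseline seizure burden is defined as a difference between average per hour seizure burden at baseline", followed by the post-dose average.
- SAP 8.2.4, the 3-hour 80% and 50% reductions: "difference between average per hour seizure burden at baseline (calculated over the 1-hour Baseline Period) and average per hour seizure burden calculated over 3 hours".
- SAP 8.2.4, ENS frequency: Baseline frequency is named before the 96-hour frequency, and the result must reach at least 50%.
- SAP 8.3.1, absolute reduction by time interval: it "is defined as the difference between the baseline average per hour seizure burden and average per hour seizure burden at evaluation periods".
- SAP 8.3.1, categorised 96-hour percentage reduction: this percentage "is defined as the difference between the average per hour baseline seizure burden and the average per hour seizure burden at the end", and the result is divided by Baseline.

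The categories in SAP 8.3.1 label a value below -25% as worsening. Two of the middle categories are "25% to ≤50%, 50% to <80" per cent, where protocol 4.2.2 has "25% to <50%, 50% to <80%, and ≥80" per cent.

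**The concern.** A variable called a reduction should be positive when burden falls. Under SAP 8.2.4 it is negative. The SAP also holds two formulas of opposite sign for one quantity, the percentage reduction over the 96 hours.

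Efficacy in this single-arm study is reported by descriptive summaries with 95% CIs, by cohort, for the combined Confirmatory Cohorts and by subgroup (SAP 3.1, 8 and 8.2.5). No hypothesis test would draw attention to a reversed direction. Programmed as written, two named secondary variables would show apparent harm where there was benefit, and they would disagree with the interval and category tables for the same babies.

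Nothing indicates that the reversal is intended. SAP Table 3.1 lists only the cause-of-seizure subgroups as a change from the protocol.

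**Working it through.** The plan states no numeric result that depends on this definition, so there is no figure to reproduce. The check applies each derivation literally to the same data.

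**Inputs.** B is the Baseline average burden in min/h. E is the 96-hour average, that is, total ENS minutes over the period divided by 96 (SAP 8.2.4). The values of B and E below are illustrative. B = 18 is borrowed from the example in SAP 8.1.2.1.

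**Formulas.**

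- SAP 8.2.4: absolute = E - B; percentage = 100 × (E - B) / B.
- SAP 8.3.1, categorised 96-hour variable: percentage = 100 × (B - E) / B.

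**Single case, B = 20 and E = 2.**

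- SAP 8.2.4: 2 - 20 = -18 min/h; 100 × (-18) / 20 = -90%.
- SAP 8.3.1: 100 × (20 - 2) / 20 = +90%, in the category of 80% or more.

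**Range, B = 18.**

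| E (min/h) | 8.2.4 absolute | 8.2.4 percentage | 8.3.1 percentage | 8.3.1 category |
|---|---|---|---|---|
| 0 | -18.0 | -100% | +100% | 80% or more |
| 1.8 | -16.2 | -90% | +90% | 80% or more |
| 3.6 | -14.4 | -80% | +80% | 80% or more |
| 9 | -9.0 | -50% | +50% | exactly 50%: two categories |
| 14.4 | -3.6 | -20% | +20% | no change |
| 36 | +18.0 | +100% | -100% | worsening |

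The magnitudes agree in every row and the signs are opposite. A seizure-free baby has a reduction of -100% under 8.2.4, and a baby whose burden doubles has +100%.

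**Is the direction in the other sections certain?** Those sections speak of a difference between two quantities without a minus sign, so the order has to be confirmed from their thresholds. If 8.1.5 were read as post-dose minus Baseline, a baby going from 20 to 36 min/h would score 100 × 16 / 20 = +80% and count as a responder, while the baby going from 20 to 2 would score -90% and fail. The requirement of at least 50% for ENS frequency and the worsening label below -25% in 8.3.1 likewise make sense only with Baseline first. SAP 8.2.4 alone spells out the subtraction, and in the other order.

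**Category limit.** With B = 18 and E = 9 the reduction is exactly 50%. SAP 8.3.1 admits it to both middle categories. Protocol 4.2.2 and the SAP's own list in 2.2.2.2 close the lower category below 50%, so the value falls in one category only.

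**The case against.** The strongest reply is that this is a mismatch between a label and a formula with little consequence. Post-dose minus Baseline is the ordinary change-from-Baseline convention. Only the sign is reversed: magnitudes, spread and CI widths are the same, and a reader could restore the direction from the output. SAP 4.5 says that all analyses are descriptive and that nothing is tested, and no decision rule in the plan reads the sign of these two variables. All of this stands, and it limits the severity. It does not make the text right, because the variables are named reductions and the SAP gives the same percentage the other sign elsewhere.

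Three stronger readings are tempting, and the documents do not support them.

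- A reader might infer that improving babies will be classified as worsening. They will not. The categories belong to a variable in 8.3.1 with its own Baseline-first derivation. The worsening label appears only if someone carries the 8.2.4 values across to those categories, and then only for improvements above 25%; smaller ones would read as no change.
- A reader might infer that 8.3.1 also gives an opposing +18 min/h for the whole 96 hours. It defines an absolute reduction only by time interval. The direct conflict over the full period concerns the percentage.
- A reader might infer that the responder results are compromised. The main secondary endpoint rests on 8.1.1 and 8.1.5, which are correctly signed.

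The overlap at 50% is a separate slip of one character. It touches only a value of exactly 50% on a continuous measure.

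**Conclusion.** The point holds as an internal inconsistency of the SAP. Followed literally, 8.2.4 reverses the sign of every non-zero value of the 96-hour absolute and percentage reductions, and so the direction of their summaries and 95% CIs. These would contradict the variables' names, the category table and the interval tables. The main responder endpoint, the 3-hour proportions, the ENS-frequency rate and the categorised table are unaffected.

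The conclusion assumes that the outputs are programmed as the text is written; a programmer might correct the sign silently, but the SAP does not tell them to. The worked values are illustrative, but the reversal does not depend on them. The severity is a minor correction, and the text is wrong as it stands.

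**What to change.** In SAP 8.2.4, define the absolute reduction as the Baseline average per hour minus the 96-hour average per hour. The percentage reduction takes its sign from that definition and needs no separate change. With B = 20 and E = 2 the results become +18 min/h and +90%, in line with 8.3.1.

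In SAP 8.3.1, end the lower middle category below 50%, as in protocol 4.2.2 and SAP 2.2.2.2.

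Renaming the two variables as change from Baseline would also remove the contradiction with the label, but it would depart from the names in protocol 4.2.1 and leave opposite signs across the tables. Correcting the subtraction is the better choice.

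The cost is a few words in the SAP and one programming specification, with no change to data collection. It should be done before the efficacy outputs are programmed and run.
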